8. RESEARCH QUESTION AND OBJECTIVES

The goal of this study is to investigate the risk of COPD exacerbations, community acquired pneumonia, and health care utilization in maintenance treatment naïve patients treated as first line therapy with Fixed Dose Combination (FDC) of Tiotropium + Olodaterol (Stiolto, 5/5 mcg), in comparison to maintenance treatment naïve patients treated with first line therapy, FDC of Fluticasone Furoate + Umeclidinium + Vilanterol (Trelegy, 100/62.5/25 mcg). Primary and Secondary analyses will be conducted for the total population and

Primary objective:

- To characterize the COPD patient population who are maintenance treatment naïve and initiated Trelegy or Stiolto as the first line therapy.
- To compare the effectiveness of Stiolto (new treatment initiation) with Trelegy (new treatment initiation) for time to the first COPD exacerbation (moderate/severe) in COPD patients who are maintenance treatment naïve.
- To compare COPD exacerbations following initiation of Stiolto (new treatment initiation) with initiation of Trelegy (new treatment initiation)

Secondary objectives:

- To compare the effectiveness of Stiolto (new treatment initiation) with Trelegy (new treatment initiation) for time to the first hospitalization of community acquired pneumonia in COPD patients who are maintenance treatment naïve.
- To assess differences between Stiolto vs Trelegy in, "all-cause" and "COPD and/or pneumonia-related", HCRU and HCRU cost (total population and sub-groups by care setting).

9. **RESEARCH METHODS**

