9.3.2 Outcomes

9.3.2.1 Primary Outcomes

The primary outcome event for effectiveness is time to first COPD exacerbation after cohort entry. The event is defined as follows:

- Severe exacerbation:
 - Hospitalization with a principal discharge diagnosis of COPD and/or
 - An emergency department (ED) visit with a discharge diagnosis of COPD
 - An inpatient admission or an ER visit with a diagnosis code for acute respiratory failure in the primary position and a COPD diagnosis code in any position
- Moderate exacerbation:
 - \circ An antibiotic for a respiratory condition dispensed \pm an OCS

Time to the first COPD exacerbation will be measured from index date until the occurrence of a hospitalization for COPD (severe exacerbation) or ED visit for COPD (severe exacerbation) or prescription of an antibiotic \pm an OCS on the same day (moderate exacerbation). Severe and moderate exacerbations were considered as a composite for main analyses. Sensitivity analyses will include stratification by exacerbation severity.

Exacerbations will be categorized as moderate or severe and a count of any (severe or moderate), severe, and moderate will be provided.

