9.7 DATA ANALYSIS

Summary measures will include standard descriptive statistics (e.g., mean, standard deviation, median and range for continuous variables; counts and percentages for categorical variables). However, for any baseline characteristics with significant differences (Standardized differences (SD) greater than 0.10 (10%)) after PSM matching, these characteristics will be included as covariates in the regression models, or we will develop interaction terms to match on or discontinue the study if major channeling (SD>10%) is observed. Basically, a two-step approach: The first step will be to characterize the patients after PS matching to see whether balance can be achieved (based on SD) and at least 2000 patients from the Stiolto cohort can be matched with at least 2000 patients in the Trelegy cohort before proceeding to the second step of doing the comparative analysis. Sensitivity analyses may be performed on a select set of covariates considered to be prognostic factors. In the event of study discontinuation, partial results (all analysis leading up to and including PSM) will be provided in a final report.

A Cox proportional hazards models will be used on the time to first COPD exacerbation with treatment as a covariate. Comparisons will be made between treatment cohorts using HR and will be presented with associated 95% CI. To account for variable lengths of follow-up observation time, population annualized results will be provided (annualized costs [e.g., Sum of total costs/Sum of total follow-up patient years for each cohort]). The annualized cost may be modelled as dependent variable in a Generalized Linear Model with treatment cohort as a covariate and the follow-up patient years as an offset for each cohort.

Comparisons will be made between treatment cohorts and will be presented with associated 95% CI. Additionally, descriptive techniques that account for the length of observation time measure will be used appropriately. Per patient per month calculations will not be performed because of bias concerns. Appropriate tests comparing the Stiolto cohort and the Trelegy cohort (e.g., standardized differences, McNamara's tests, paired t-tests, sign tests) will be used based on the distribution of the measure. Patients not matched will be excluded from the post-match analysis.

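### The primary comparison of exacerbations has no specified inferential model, and the example between-cohort tests take no account of unequal on-treatment time

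*Combined protocol and SAP*

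**What the plan says.** Section 8 gives two comparative primary objectives. One is time to first exacerbation. The other is separate: "To compare COPD exacerbations following initiation of Stiolto (new treatment initiation) with initiation of Trelegy (new treatment initiation". Section 9.3.2.1 supplies the matching variable: "a count of any (severe or moderate), severe, and moderate will be provided".

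On methods, Section 9.7 states "A Cox proportional hazards models will be used on the time to first COPD exacerbation with treatment as a covariate", and Section 9.7.1 repeats Cox as the analysis of the primary objective. The only model with a follow-up offset is optional and is for cost: "The annualized cost may be modelled as dependent variable in a Generalized Linear Model". Between-cohort tests appear in a list introduced as examples, which starts with standardized differences and a McNemar-type test and goes on: "paired t-tests, sign tests) will be used based on the distribution of the measure".

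Section 9.7 recognises unequal follow-up in two places: "To account for variable lengths of follow-up observation time, population annualized results will be provided", where costs are the only example, and "descriptive techniques that account for the length of observation time measure will be used appropriately". It rules out per-patient-per-month calculations.

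Section 9.3.1 censors at discontinuation, switch, disenrollment, 12 months or the end of the study period. In one of its lists, adding an ICS ends follow-up for the Stiolto cohort only. Sections 9.1 and 9.2.2 also end follow-up at the first outcome event; the lists in Section 9.3.1 do not.

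**The concern.** On-treatment follow-up lasts as long as the patient stays on the drug, so the two members of a matched pair will usually be observed for different lengths of time. If persistence differs between the drugs on average, the one that patients stay on longer accrues more exacerbations at the same underlying rate and looks worse. A paired comparison of counts, or of the proportion with any event, cannot separate this from a difference in risk.

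At stake is the interpretation of one of the two comparative primary objectives. With no estimator fixed in advance, the method can be chosen after the data are seen. If the choice fell on one of the example tests, its p-value would partly measure persistence and could disagree with the Cox result for no clinical reason.

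**Working it through.** **1. Matching objectives to methods.** The plan states no figure for the exacerbation-count comparison, so there is none to reproduce. (The claim of at least 80% power in Section 9.5 names no hazard ratio or event fraction and does not bear on this point.)

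| Comparison | Method named | Uses follow-up time? |
|---|---|---|
| Time to first exacerbation | Cox (9.7, 9.7.1) | Yes |
| Cost | GLM with patient-years offset, optional (9.7) | Yes |
| Any measure, by its distribution | McNemar-type, paired t, sign, as examples (9.7) | No |
| Exacerbation counts | None; counts to be provided (9.3.2.1) | Not stated |

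It is an inference that the paired tests would act on unscaled counts. It is the natural one: a cohort-level annualized figure is one number per cohort and cannot enter a paired test, and per-patient-per-month values are ruled out.

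**2. Inputs.** From the documents: 3,018 pairs (9.5) and at most one year of follow-up (9.3.1). Two-sided 0.05 is read from the 95% intervals. Assumed, because the documents give none: a true rate r equal in both arms, 0.5 to 1.0 per year; dispersion k (gamma frailty variance) of 1, with 2 as a variant; exponential time to stopping, capped at one year and unrelated to risk; mean on-treatment time near 0.5 years.

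**3. Formula for the paired t-test.** For follow-up T with scale s capped at 1 year:

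- E[T] = s(1 − e^(−1/s))
- E[T²] = 2s²[1 − e^(−1/s)(1 + 1/s)]
- Var(N) = r·E[T] + r²[(1+k)E[T²] − E[T]²]
- δ = r(E[T_B] − E[T_A]) / √[(Var_A + Var_B)/3018]
- rejection = Φ(δ − 1.96) + Φ(−δ − 1.96)

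*Example 1:* r = 0.5, k = 1, means 0.475 and 0.50 years (E[T²] 0.344 and 0.3725).
- Var_A = 0.2375 + 0.25(0.688 − 0.2256) = 0.353
- Var_B = 0.25 + 0.25(0.745 − 0.25) = 0.374
- δ = 0.0125/0.01552 = 0.805, so rejection is 12.7%.

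*Example 2:* r = 1.0, k = 1, means 0.45 and 0.50 years (E[T²] 0.316 and 0.3725).
- Var_A = 0.45 + (0.633 − 0.2025) = 0.880
- Var_B = 0.50 + (0.745 − 0.25) = 0.995
- δ = 0.05/0.02493 = 2.006, so rejection is 51.8%.

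**4. Simulation,** 1,000 replicates per setting (standard error about 0.7 points at 5%). Ranges span r = 0.5 and 1.0.

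| Mean time, years | Ratio | k | Paired t | Sign | McNemar, any event | Poisson with offset, robust variance |
|---|---|---|---|---|---|---|
| 0.50 vs 0.50 | 1.00 | 1 | 5.1-5.2% | 4.8-5.6% | 4.4-5.6% | 4.5-4.8% |
| 0.475 vs 0.50 | 1.05 | 1 | 12.9-16.9% | 13.0-16.0% | 13.8-14.5% | 4.6-5.1% |
| 0.45 vs 0.50 | 1.11 | 1 | 35.3-50.9% | 35.9-49.9% | 35.7-48.3% | 5.1-5.2% |
| 0.45 vs 0.50 | 1.11 | 2 | 27.8-40.1% | 26.3-38.7% | 26.3-36.7% | 3.8-5.7% |
| 0.40 vs 0.50 | 1.25 | 1 | 90.9-98.4% | 91.1-98.1% | 91.4-98.3% | 4.6-4.9% |

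A second set of 600 runs per setting (r = 0.5 and 0.8, k = 1) used scales of 0.60 against 0.66 and 0.72. These give means of 0.487 against 0.515 (5.8% longer) and 0.540 (11.1% longer). The paired t-test rejected in 14.8-18.0% and 39.2-48.3%.

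**5. Does the follow-up conflict change this?** If follow-up ends at the first event (9.1, 9.2.2), each count is at most 1 and there are no recurrent counts to model. Whether a patient has any event on treatment is the same under either rule, so the McNemar column holds under both. The count objective itself does not: it needs follow-up that continues past the first event.

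**The case against.** The case against has real force.

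- **The test list is illustrative.** It covers every measure, includes standardized differences (a balance statistic), and is not tied to exacerbation counts. A rate model is not excluded.
- **The plan centres on first events.** Sections 9.3.2.1 and 9.5 make time to first exacerbation the primary outcome, and Section 9.7.1 gives Cox for the primary objective. Counts are only to be provided, which may mean descriptively.
- **Variable follow-up is recognised in general terms.** A rate per patient-year with a confidence interval would fit the wording of Section 9.7.
- **The visible text may be incomplete.** Section numbering runs from 9.7.1 to 9.7.3, so absence can be asserted only for what is shown.
- **The rejection rates rest on assumed inputs.** If persistence is similar, there is no inflation.

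These points defeat a stronger reading. A reader might infer that the plan commits to paired tests on raw counts and that a primary p-value is therefore invalid. The documents do not say that, and no such p-value is shown to be planned.

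What remains is narrower. An exacerbation comparison is listed as a primary objective in its own right, no estimator is given for it, every example test ignores exposure time, and the provisions for variable follow-up are summaries without a test, model or variance method.

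**Conclusion.** The concern holds as a gap in the analysis plan with a foreseeable consequence. The visible text specifies no inferential model for the third primary objective. If the example paired tests filled that gap, type I error would rise whenever mean on-treatment time differed between the drugs at equal exacerbation rates. With 3,018 pairs and dispersion 1, rejection is about 13-18% for a 5-6% difference in time and 35-51% for about 11%, against 5% with equal time. Higher dispersion softens this: 26-40% at 11% with dispersion 2.

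The direction follows from the design: at equal rates, more time means more events. The size does not, because on-treatment time, event rate and dispersion are all assumed. The figures illustrate sensitivity and do not forecast this study's error rate.

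**What to change.** - For any, moderate and severe exacerbation counts, specify a negative binomial model, or Poisson with robust variance, with log on-treatment person-time as offset and pair-clustered variance. Report the rate ratio with its 95% CI. (The simulation tested the robust Poisson form on independent pairs; the negative binomial form and pair clustering were not simulated.)
- Use the same offset for any between-cohort comparison of HCRU counts.
- Reconcile Sections 9.1 and 9.2.2 with Section 9.3.1, so that follow-up for counts does not end at the first event.
- State that the offset removes the person-time artefact but not bias from discontinuation or switching related to exacerbation risk. The ICS-addition rule, named for the Stiolto cohort only, makes this worth saying.

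The data are unchanged. The cost is a little more programming.

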9.7.1 Main analysis

Analyses will be presented comparing Stiolto vs Trelegy overall after PSM matching and stratified as follows if the sample size allows (at least 15% in each strata):

• Low history of exacerbation: 0 inpatient (i.e., severe exacerbations) and 0-1 outpatient events (i.e., moderate exacerbations)

Proprietary confidential information © 2022 Boehringer Ingelheim International GmbH or one or more of its affiliated companies

• High history of exacerbation: ≥1 inpatient (i.e., severe exacerbations) or ≥2 outpatient events (includes ED)

We will describe the formation of the study cohort. Patient characteristics at baseline in patients treated with Stiolto and patients treated with Trelegy will be assessed separately using standard descriptive statistics.

Propensity scores including both pre-specified and data-derived variables will be then calculated. Balance of patient characteristics between the cohorts will be described before and after propensity score application and compared using standardized differences. For each Stiolto patient, a Trelegy patient with the closest available propensity score will be selected. Nearest neighbor matching method with a caliper of 0.2 will be utilized. Standardized differences greater than 0.10 (10%) will be taken to indicate imbalance, and these variables will also be included in outcome models, categorized as appropriate.

For the analysis of the primary objective, a Cox proportional hazard regression model will be used to perform an as-treated analysis that assesses the effect of first line maintenance medication with Stiolto versus the first line maintenance medication with Trelegy on the time to first COPD exacerbation. This estimates the HR of a COPD exacerbation associated with Stiolto use relative to Trelegy use, along with 95% CI. Based on the days' supply post index date, allowing a grace period of 45 days following the end of days' supply to account for intermittent use.

Stratified analyses will be using the same approach as the main analysis. Calculation of propensity scores will be repeated within the subset of the cohort with available results to create weighted populations suitable for these stratified analyses.

The analysis of the secondary objective related to the risk of pneumonia will also be assessed using Cox proportional hazard regression models with an as-treated approach, like that of the primary analysis.

In terms of HCRU, we will be presenting continuous and categorical variables using standard descriptive statistics to describe total visits and total costs related to inpatient, outpatient, and emergency care as well as distinct medications used, and pharmacy costs. Utilization and costs will be stratified to facilitate comparison between Stiolto and Trelegy and presented by individual setting and cost will also be presented as a composite. All-cause and COPD and/or pneumonia specific cost and utilization characteristics will be described separately.

Page 35 of 47

c38026921-01

Proprietary confidential information © 2022 Boehringer Ingelheim International GmbH or one or more of its affiliated companies

9.7.3 Safety Analysis

Data is anonymized and extracted, analyzed, validated, and reported in aggregate. There is no potential that any employee of BI or agent working on behalf of BI will access individual patient data where adverse events is identified during data compilation, data reporting or data analysis.

Proprietary confidential information © 2022 Boehringer Ingelheim International GmbH or one or more of its affiliated companies

9.8 QUALITY CONTROL

All programming will be quality controlled by two-step code checking by All results generated will be reviewed internally by two co-investigators separately prior to finalization.

develops study approaches of sound scientific design that meet clinically stringent review. Researchers develop detailed protocols that include definitions, codes, analyses, and table shells. The coding strategy is then reviewed by a clinical team member for validity and relevance to ensure potential outlying issues are identified and addressed. The protocol further provides and and an opportunity to solidify research questions and address any potential gaps in information

incorporates meticulous quality assurance checks during data set construction to generate the most accurate data set. Our analysts perform record-level verification of all data elements, double-program certain portions of the data set, program data edit checks, visually review raw claims data against the constructed data elements and review the analysis to assess the validity of results.

Results will be verified by the study. and BI research team assigned to the

Proprietary confidential information © 2022 Boehringer Ingelheim International GmbH or one or more of its affiliated companies

9.9 LIMITATIONS OF THE RESEARCH METHODS

As with all studies utilizing claims data, there are certain limitations that should be noted. The presence of a claim for a filled prescription or prescription absent a claim does not indicate that the medication was consumed or that it was taken as prescribed. Medications filled over the counter or provided as samples by the physician will not be observed in the claims data. Patients with commercial health insurance may be different from those with non-commercial or without (commercial) health insurance, and hence study results may not be generalizable to the overall population. Population aged 65 years and older might be underrepresented, which may affect external validity in the case of Medicare, Medicare Advantage or Medicaid patients. Socioeconomic data is not available. Smoking status information during the study period is not available in this data source. Since unmatched patients will be excluded, the results may not be generalizable to all patients. Some study measures and outcomes will include missing data and hence reduce the sample size. This real-world evidence study lacks controls available with RCTs. Patient misclassification, missing data, objective and reliable measurement of patient outcomes, and lack of detailed information regarding subjects' clinical history or clinical status during the study timeframe may undermine the accuracy of our study results. In the absence of randomization, confounding by indication could be an issue. Controlling via PSM should limit this bias but can control only for measured covariates and may produce estimates that are impacted by residual confounding. This is of particular importance in the case of lifestyle factors that are less critical to insurance billing and thus poorly captured in claims data.

There is the possibility of information bias due to misclassification of the outcomes or exposure or missing data as prescriptions dispensed by a pharmacy but not taken by patients could lead to misclassification of exposure. Pharmacy dispensing data does bring us one step closer to patient use than physician prescribing given that the patient has taken the effort to obtain the medication as instructed, however, information such as indication can only be inferred based on diagnostic patterns.

Finally, we cannot exclude the possibility of unmeasured differences in exacerbation risk across exposure groups. Data on several relevant confounders (e.g., Body mass index, smoking habits, symptom scores), as well as data from spirometry on lung function will not be available for analysis. Although certain bias analysis can be planned but they are limited by the strength of the assumptions they rely on. An impact of residual confounding caused by these unmeasured factors cannot be ruled out. Further, we cannot exclude the possibility that patients may have gone on to develop outcomes later beyond the study period. We will conduct bias analysis as appropriate to address these concerns.

001-MCS-90-118_RD-23 (2.0) / Saved on: 02 Jul 2020

Proprietary confidential information © 2022 Boehringer Ingelheim International GmbH or one or more of its affiliated companies

9.10 OTHER ASPECTS

Not applicable.

10 PROTECTION OF HUMAN SUBJECTS

The study will be carried out in compliance with the protocol, the principles laid down in the Declaration of Helsinki, Guidelines for Good Pharmacoepidemiology Practice (GPP), and the relevant BI Standard Operating Procedures (SOPs).

The rights of the investigator and of the sponsor about publication of the results of this study are described in the investigator contract. As a rule, no study results should be published prior to finalization of the study report.

10.1 STUDY APPROVAL, PATIENT INFORMATION, AND INFORMED CONSENT

This NIS is a retrospective database analysis of existing data and is IRB exempt as there is no patient informed consent required for the study.

10.2 STATEMENT OF CONFIDENTIALITY

No patient's identity or medical records will be disclosed for the purposes of this study except in compliance with applicable law.

11. MANAGEMENT AND REPORTING OF ADVERSE EVENTS/ADVERSE REACTIONS

Data is anonymized and extracted, analyzed, validated, and reported in aggregate. There is no potential that any employee of BI or agent working on behalf of BI will access individual patient data where adverse events is identified during data compilation, data reporting or data analysis.

Proprietary confidential information © 2022 Boehringer Ingelheim International GmbH or one or more of its affiliated companies

12. PLANS FOR DISSEMINATING AND COMMUNICATING STUDY RESULTS

The rights of the investigator and of the sponsor regarding publication of the results of this study are described in the investigator contract. As a rule, no study results should be published prior to finalization of the study report.

